3 INVESTIGATIONAL PLAN

3.1 Study Design

This is an unblinded randomized controlled trial.

Women randomized to group 1 will meet with the genetic counselor as scheduled, then complete the knowledge and decisional conflict assessments. Women randomized to group 2 will self-administer the decision aid within the app, then complete the knowledge and decisional conflict assessments. Following this, they will meet with the genetic counselor as scheduled; following this appointment, they will again complete the same assessment. Additionally, prior to and following meeting with the genetic counselor, women in group 2 will be asked whether they would or did find it helpful to meet with a genetic counselor.

Genetic counselors will be educated prior to study initiation that their counseling should not be modified based on group assignment; generally, women < 35 years old received abbreviated counseling on aneuploidy screening and testing options and those \geq 35 years old received more extensive counseling. Within ACMG guidelines, all screening tests are available to all women; cost information and insurance coverage information on available tests will also be provided prior to final decision making. Women will then undergo their screening or testing modality of choice. All study participation and completion of initial screening will be completed within the single encounter.

3.2 Allocation to Treatment Groups and Blinding (if applicable)

Via a coin-flip algorithm within the decision aid application, women will be randomly assigned to group 1 (control group) or group 2 (decision aid group)

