3.3 Study Duration, Enrollment and Number of Subjects

Study duration for each participant is limited to the single study visit during which patients are enrolled, complete questionnaires, and complete genetic counseling. 200 participants will be enrolled. This is anticipated to take approximately 12 months.

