3.4 Study Population

English and Spanish-speaking women with a singleton gestation at less than 22 weeks who are scheduled to meet with a genetic counselor at one of three prenatal diagnosis clinics for a discussion of aneuploidy screening and testing options are eligible for participation.

Exclusion criteria include: multiple gestations, prior abnormal ultrasound in the current pregnancy, or prior aneuploidy screening in the current pregnancy.

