4.2 Intervention

Following informed consent, the app was accessed and a study ID assigned. Via a coin-flip algorithm within the app, women were randomly assigned to group 1 (control group) or group 2 (decision aid group). As it was not pragmatic for this study, randomization assignment was not blinded. Investigators were not involved in developing the randomization scheme within the app. All women completed an initial demographic and knowledge questionnaire immediately following randomization via self-administered assessments within the app.

Study flow is described in the below figure. Women randomized to group 1 met with the genetic counselor as scheduled, then completed the knowledge and decisional conflict assessments. Women randomized to group 2 self-administered the decision aid within the app, then completed the knowledge and decisional conflict assessments. Following this, they met with the genetic counselor as scheduled; following this appointment, they again completed the same assessment.

Additionally, prior to and following meeting with the genetic counselor, women in group 2 were asked whether they would or did find it helpful to meet with a genetic counselor.

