6 STATISTICAL CONSIDERATION

6.1 Sample size calculation

An initial power calculation was performed using historical data from the maternal serum screening questionnaire assuming a standard deviation of 3 questions; to achieve 80% power with a 2-tailed alpha of 0.05, 92 women would be needed in each arm. Assuming a 7.5% fall-out rate from women with nonviable pregnancies, 100 patients were required in each arm for a total enrollment of 200 women.

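### Coin-flip allocation leaves balance on age group, clinic and language to chance, and the primary comparison in section 6.2 does not adjust for these recorded factors

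*Combined protocol and SAP*

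**What the plan says.** Allocation is described twice. Section 3.2 reads: "Via a coin-flip algorithm within the decision aid application, women will be randomly assigned to group 1". Section 4.2 describes the same coin flip, in the past tense, and adds: "Investigators were not involved in developing the randomization scheme within the app". Neither section mentions blocks, strata or minimisation.

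On numbers, section 3.3 states "200 participants will be enrolled", and section 6.1 states "100 patients were required in each arm for a total enrollment of 200 women", built up from "92 women would be needed in each arm".

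Three features of the design could bear on the score:
- **Age.** Section 3.1 says that, generally, "women < 35 years old received abbreviated counseling on aneuploidy screening and testing options", with more extensive counseling from age 35.
- **Clinic.** Section 3.4 has women seen "at one of three prenatal diagnosis clinics".
- **Language.** Women take part in English or Spanish.

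Section 5 collects age, preferred language and site of enrollment. In section 6.2, age appears only in the baseline comparisons (mean age, and advanced maternal age as a category). Site and language do not appear there at all. The between-arm knowledge comparison is a Wilcoxon rank-sum test with no covariates or strata.

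**The concern.** The primary contrast in section 2.1 sets group 2 after the decision aid against group 1 after counseling. How much counseling lies behind the group 1 score depends in part on how many of those women are 35 or older. The synopsis calls the comparator an abbreviated genetic counseling visit, so the age mix also affects what the result means. Clinic and language are plausible further influences on the score.

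With unrestricted allocation and an unadjusted test, score variation due to these factors stays in the error term, and any chance imbalance goes straight into the estimate. What is at stake is precision against a 1-question limit, and how convincing the result is if the arms happen to differ.

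**Working it through.** **Inputs.** From section 6.1: 92 evaluable per arm, 7.5% fall-out, 100 per arm, SD 3, and "to achieve 80% power with a 2-tailed alpha of 0.05". From section 3.3: 200 in total. From section 2.1: margin 1 question of 12. The documents do not give the share of women aged 35 or older, or the effect of age on the score; both are assumed below and shown as ranges.

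**1. The plan's own figures.** 92/(1 − 0.075) = 99.5, so 100 per arm reproduces. The 92 does not follow from margin 1 and SD 3. The formula 2 × 9 × (1.960 + 0.842)²/1² gives 142 per arm; 92 corresponds to a difference of 3 × 2.802 × √(2/92) = 1.24. That is a separate matter. Power is therefore shown below for both 1.24 and 1.

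**2. Arm sizes under a fair coin, Binomial(200, 0.5).**
- Exactly 100/100: 5.6%.
- Central 95% range: 86 to 114.
- Smaller arm below 92 at enrollment: 22.9%.
- With 7.5% loss per woman, at least one arm below 92 evaluable: 85%. With the split fixed at 100/100 this is still 56%.

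**3. What unequal arms cost.** Power = Φ(Δ/(3√(1/n₁ + 1/n₂)) − 1.96), with each arm multiplied by 0.925.

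| Split | Δ = 1.24 | Δ = 1 |
|---|---|---|
| Fixed 100/100 | 80.2% | 62.1% |
| Average over coin flips | 80.0% | 61.8% |
| 86/114 | 79.4% | 61.2% |

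The loss is about 0.2 points on average and 0.8 to 0.9 at the edge of the 95% range.

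**4. Chance imbalance in age.** With 100 per arm, the SD of the difference in shares is √(2p(1 − p)/100). For p from 10% to 50%, the 95% limit is 8 to 14 percentage points, and a difference of 10 points or more has probability 2% to 16%. A 14-point imbalance with a 1-question age effect moves the arm difference by 0.14 × 1 = 0.14 question (0.07 to 0.28 for effects of 0.5 to 2).

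**5. Validity.** Noninferiority was simulated with a 95% interval on the mean difference, 185 evaluable women, half aged 35 or older, age effects of 0, 1 and 2 questions, and 40,000 runs per setting. Type I error under the coin flip was 2.5% to 2.7% against a nominal 2.5%. Stratifying allocation by age without adjusting the analysis changed power by less than 1 point. At a 2-question effect it also made the test conservative (type I error 1.9%).

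**6. What adjustment gains.** Assume p = 0.5 and an age effect of d questions.
- *Same effect in both arms.* Share of variance removed = 0.25d²/9, which is 2.8% for d = 1 and 11.1% for d = 2.
- *Effect in group 1 only*, since group 2 is scored before counseling. The share is at most half: 0.25d²/(2 × 9) = 1.4% to 5.6%. A single age term common to both arms would recover less than this ceiling.

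Power at 92 per arm, with the variance multiplied by (1 − share):

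| | Δ = 1 | Δ = 1.24 |
|---|---|---|
| Unadjusted | 61.8% | 80.0% |
| Same effect, d = 1 to 2 | 63.0% to 66.9% | 81.1% to 84.4% |
| Group 1 only (ceiling), d = 1 to 2 | 62.4% to 64.3% | 80.5% to 82.2% |

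**The case against.** A reader might infer that a coin flip cannot deliver the required 100 per arm. The documents do not support that. An equal split is the expected result, section 6.1 gives 100 per arm as a sample-size target, and section 3.3 fixes only the total. No passage makes exact equality a condition. The 85% chance of an arm ending below 92 also misleads: fall-out alone gives 56%, and the count says little about power.

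A reader might also infer that the arms will be unbalanced, or the test invalid. Simple randomization balances every factor in expectation, the test already allows for chance imbalance, and the simulated error rate stays near nominal. The 16% chance of a 10-point age difference is the top of the range, reached only if half the women are 35 or older.

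Two further objections stand. A coin flip is the least predictable allocation, which is a real merit in an unmasked trial, so blocks are a trade-off and not a correction. And if age acts only through counseling, the effect is confined to group 1 and the gain from adjustment at least halves.

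None of this justifies leaving recorded factors out of the primary comparison. Adjustment works as well after a coin flip as after stratified allocation.

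**Conclusion.** The point holds as a modest matter of precision and credibility, not of bias. The coin flip is valid, and unequal arm sizes cost under 1 point of power. The improvable part is the unadjusted primary comparison. Adjusting for age group is worth roughly 1 to 5 power points if half the women are 35 or older and age shifts the score by 1 to 2 questions equally in both arms. If the shift is in group 1 only, the gain is at most about 0.5 to 2.5 points. A smaller share of older women or a weaker age effect would reduce it. Clinic and language may add something, but the documents give no basis for putting a figure on it.

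**What to change.** In section 6.2, prespecify the primary knowledge comparison adjusted for age group (under 35; 35 or older), clinic and preferred language. One suitable form is a linear model that gives the adjusted arm difference with its confidence interval, read against the 1-question limit. Add site and language to the baseline table. All three factors are already collected, so the cost is a few lines of text and no new data. The change should be fixed before outcomes are compared by arm.

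If allocation can still be changed, 1:1 blocks of randomly varying size within the app, stratified by age group and clinic, are an optional addition. That makes 2 × 3 = 6 strata, averaging 200/6 ≈ 33 women each. The price is slightly more predictable assignment in an unmasked trial and a change to allocation code that the investigators did not develop. Because section 4.2 describes assignment as already done, this may no longer be possible. If strata are used, the analysis must include them.

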3.3 Study Duration, Enrollment and Number of Subjects

Study duration for each participant is limited to the single study visit during which patients are enrolled, complete questionnaires, and complete genetic counseling. 200 participants will be enrolled. This is anticipated to take approximately 12 months.

3.4 Study Population

English and Spanish-speaking women with a singleton gestation at less than 22 weeks who are scheduled to meet with a genetic counselor at one of three prenatal diagnosis clinics for a discussion of aneuploidy screening and testing options are eligible for participation.

Exclusion criteria include: multiple gestations, prior abnormal ultrasound in the current pregnancy, or prior aneuploidy screening in the current pregnancy.

4 STUDY PROCEDURES

4.1 Screening procedure

[figure not shown]
For the randomized trial, charts of women scheduled to see a genetic counselor for a discussion of aneuploidy screening or testing were screened for eligibility and eligible women were contacted within a week before their visit by telephone by trained study personnel. Women who indicated in the medical record that they preferred Spanish were contacted by Spanish-speaking study personnel. Those who agreed to participate were asked to arrive early for their appointment to be enrolled in the study.

4.2 Intervention

Following informed consent, the app was accessed and a study ID assigned. Via a coin-flip algorithm within the app, women were randomly assigned to group 1 (control group) or group 2 (decision aid group). As it was not pragmatic for this study, randomization assignment was not blinded. Investigators were not involved in developing the randomization scheme within the app. All women completed an initial demographic and knowledge questionnaire immediately following randomization via self-administered assessments within the app.

Study flow is described in the below figure. Women randomized to group 1 met with the genetic counselor as scheduled, then completed the knowledge and decisional conflict assessments. Women randomized to group 2 self-administered the decision aid within the app, then completed the knowledge and decisional conflict assessments. Following this, they met with the genetic counselor as scheduled; following this appointment, they again completed the same assessment.

Additionally, prior to and following meeting with the genetic counselor, women in group 2 were asked whether they would or did find it helpful to meet with a genetic counselor.

4.3 Subject Completion/ Withdrawal procedures

Participants are instructed to inform their enrolling research study personnel should they desire to withdraw and participation could be terminated at that time.

5 STUDY EVALUATIONS AND MEASUREMENTS (how measurements will be made)

- Demographic characteristics will be abstracted from questionnaires and medical chart
 - o Age
 - o Race/ethnicity
 - o Preferred language
 - o Parity
 - o Gestational age
 - o Site of enrollment
 - o Insurance status
 - o Employment status
 - o Education level
 - o History of genetic counseling in prior pregnancy
- Baseline knowledge assessment
 - o This will be assessed via the previously described modified MSSKQ questionnaire prior to intervention
- Knowledge and decisional conflict scores as described will be collected via self-administered questionnaires embedded within the application

6 STATISTICAL CONSIDERATION

6.1 Sample size calculation

An initial power calculation was performed using historical data from the maternal serum screening questionnaire assuming a standard deviation of 3 questions; to achieve 80% power with a 2-tailed alpha of 0.05, 92 women would be needed in each arm. Assuming a 7.5% fall-out rate from women with nonviable pregnancies, 100 patients were required in each arm for a total enrollment of 200 women.

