2 STUDY OBJECTIVE

2.1 Primary Objective

The primary hypothesis of this study was that knowledge scores of women in group 2 following completion of the decision aid only would not be inferior to knowledge scores of women in group 1 following genetic counseling. A noninferiority limit of 1 question different on a 12 point questionnaire was selected as a clinically relevant difference.

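### The 92 women per arm in section 6.1 gives about 61% power, not 80%, for the 1-question noninferiority limit with SD 3; 80% would need about 142 per arm

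*Combined protocol and SAP*

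**What the plan says.** The primary hypothesis (section 2.1, Primary Objective) is one of noninferiority. Knowledge scores in group 2 after the decision aid alone "would not be inferior to knowledge scores of women in group 1 following genetic counseling". The same section fixes the margin: "A noninferiority limit of 1 question different on a 12 point questionnaire was selected as a clinically relevant difference".

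Section 6.1 (Sample size calculation) draws on historical data for the maternal serum screening questionnaire, "assuming a standard deviation of 3 questions", and concludes: "to achieve 80% power with a 2-tailed alpha of 0.05, 92 women would be needed in each arm". It then allows for losses ("Assuming a 7.5% fall-out rate from women with nonviable pregnancies") and arrives at the enrolment target: "100 patients were required in each arm for a total enrollment of 200 women".

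Section 6.1 does not state the difference or margin used, the assumed true difference, or the test behind the calculation. The Protocol Synopsis and section 6.2 (Statistical Methods) both plan a Wilcoxon rank-sum comparison of knowledge, without baseline adjustment.

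**The concern.** A noninferiority sample size depends on the margin, the SD, the significance level, the power and the assumed true difference. The plan gives the first four, and equality of the arms is the usual default for the fifth. A limit of 1 against an SD of 3 is a standardized margin of one third, and 92 per arm is too few to give 80% power for that at a two-sided 0.05 level.

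This is the trial's primary hypothesis. If the power is overstated, the trial is more likely than advertised to end without showing noninferiority even when the aid is as good as counseling. A reader who trusts the 80% figure could then take an inconclusive result as evidence against the aid.

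**Working it through.** **Inputs**

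- Limit d = 1 question (section 2.1)
- SD = 3 questions (section 6.1)
- Power 80%, so z = 0.842 (section 6.1)
- Two-tailed alpha 0.05, so z = 1.960; for noninferiority this is one-sided 0.025 (section 6.1)
- Equal arms, 92 evaluable in each (section 6.1)
- True difference 0 (assumption; the plan states none)

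**Step 1. The plan's own figures.** The loss allowance reproduces: 92 / (1 − 0.075) = 99.5, so 100 per arm and 200 in total. The 92 itself does not.

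**Step 2. Sample size from the stated inputs.**

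n per arm = 2 × (1.960 + 0.842)² × SD² / d² = 2 × (1.960 + 0.842)² × 9 / 1 = 141.3, so **142**. The noncentral t calculation gives 142.2, so 143. With the plan's loss allowance, 142 / 0.925 = 153.5, so 154 per arm or 308 in total.

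**Step 3. Power at the stated sample size.**

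The standard error of the difference is 3 × √(2/92) = 0.442. Power = Φ(1/0.442 − 1.960) = Φ(0.301) = **61.8%**; by noncentral t it is **61.4%**.

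**Step 4. Other readings with limit 1 and SD 3.**

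| Reading | n per arm for 80% power | Power at 92 per arm |
|---|---|---|
| Two-tailed 0.05 (as stated) | 142 (t: 143) | 61.8% (t: 61.4%) |
| One-sided 0.05 | 112 | 73.1% (t: 72.8%) |
| One-sided 0.10 | 82 | – |
| Rank-sum, efficiency 0.955 (normal data) | 148 | about 60% |
| Rank-sum, efficiency 0.864 (worst case) | 164 | about 56% |
| Equivalence (two one-sided tests at 0.05 / 0.025) | 155 / 190 | – |
| One-sample or paired | 71 | – |

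None of these gives 92. If nobody is lost and all 100 per arm are evaluable, power is 65% at two-tailed 0.05 and 76% at one-sided 0.05.

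**Step 5. What would give 92.** Each of the following does, and none is in the documents:

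- A difference of (1.960 + 0.842) × 0.442 = 1.24 questions at SD 3. By t, a difference of 1.25 gives 91.4, so 92.
- An SD of 1 / [(1.960 + 0.842) × √(2/92)] = 2.42 at a limit of 1. By t, an SD of 2.4 gives 92.
- A true advantage of 1.24 − 1 = 0.24 question for the decision aid.
- Baseline adjustment with a correlation of √(1 − 92/141.3) = 0.59, which does not fit the planned unadjusted rank-sum test.

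**Step 6. What 92 per arm means for the result.** If noninferiority is judged by a 95% confidence interval for the mean difference (an assumption; the plan gives no interval rule), the half-width is 1.960 × 0.442 = 0.87 question. The observed difference would have to be better than −1 + 0.87 = −0.13 question.

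**The case against.** The best defence is that section 6.1 never names the difference it was powered for, and that its SD may be on another scale. The SD is attributed to historical data on the maternal serum screening questionnaire, whereas the limit applies to the 12-question modification of it. The documents do not give the length of the parent instrument. If that length is treated as an assumption and SD 3 is rescaled in proportion to 12 items, the t calculation gives:

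| Assumed parent length | Rescaled SD | n per arm |
|---|---|---|
| 12 | 3.00 | 143 |
| 13 | 2.77 | 122 |
| 14 | 2.57 | 105 |
| 15 | 2.40 | 92 |
| 16 | 2.25 | 81 |

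So 92 could come from a sound calculation with an unreported conversion.

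Part of this stands. How the 92 was reached cannot be known from the documents, and the 61% holds only if SD 3 applies to the 12-question score. It does not rescue the text. The plan gives both the SD and the limit in questions and mentions no conversion. If an SD of 2.4 was used, section 6.1 misstates it. If a difference of 1.25 was used, the trial was sized for more than its own limit, and power at that limit is still about 61%. Every route leaves section 6.1 needing a correction or a missing assumption.

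It is also fair to say that the −0.13 threshold rests on an interval rule the plan does not state, and that the baseline correlation of 0.59 has no source in the documents. The conclusion depends on neither.

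**Conclusion.** The concern holds. The stated inputs require 142 women per arm, and 92 is about 35% short of that (50/142). The shortfall in power is about 19 percentage points (80% against 61%). If the arms are truly equal, the chance of missing noninferiority is about 39% instead of 20%. The planned rank-sum test makes this slightly worse under normality, and relaxing to one-sided 0.05, which contradicts section 6.1, still reaches only 73%. The result rests on the 1-question limit being the difference intended, SD 3 applying to the 12-question score, and no true difference between arms. The first two are the natural reading of sections 2.1 and 6.1; the third is the usual default.

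**What to change.** First establish which difference, which SD (and on which scale), which true difference and which test produced 92, and state them in section 6.1. If any differs from a 1-question limit and SD 3, reconcile it with section 2.1.

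If those inputs stand, section 6.1 should read along these lines: *With 92 evaluable women per arm, SD 3, a 1-question noninferiority limit, one-sided alpha 0.025 and no true difference, power is about 61%; 80% power would need 142 per arm.*

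N = 200 can stay. The cost is one paragraph and a less favourable stated power, with no extra patients.

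Optionally, section 6.1 can note that a baseline-adjusted primary analysis would bring power back to about 80% at 92 per arm if baseline and post-intervention scores correlate at about 0.6. The data would be available, since section 4.2 has all women complete a baseline knowledge questionnaire. It would mean replacing the unadjusted rank-sum test as the primary analysis, and the correlation would have to be justified.
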